10.4.1.4 Abnormal Laboratory Values

Laboratory test results will be recorded on the laboratory results pages of the eCRF, or appear on electronically produced laboratory reports submitted directly from the central laboratory, if applicable.

Any laboratory result abnormality fulfilling the criteria for a SAE or EOSI should be reported as such, and recorded in the AE eCRF.

Any laboratory result abnormality of CTCAE Grade 4 or 5 should be recorded as an SAE in the AE eCRF.

A clinical laboratory abnormality is considered clinically significant and should be documented as an AE if not refuted by a repeat test to confirm the abnormality and **any** one or more of the following conditions is met:

- Accompanied by clinical symptoms
- Requiring a change in concomitant therapy (eg, addition of, interruption of, discontinuation of, or any other change in a concomitant medication, therapy or treatment).
- The abnormality suggests a disease and/or organ toxicity
- The abnormality is of a degree that requires active management (eg, change of dose, discontinuation of study drug, more frequent follow-up assessments, further diagnostic investigation, etc.)

This applies to any protocol and non-protocol specified safety and efficacy laboratory result from tests performed after the first dose of study medication that falls outside the laboratory reference range and meets the clinical significance criteria.

This does not apply to any abnormal laboratory result that falls outside the laboratory reference range but that does not meet the clinical significance criteria (these will be analyzed and reported as laboratory abnormalities), those that are considered AEs of the type explicitly exempted by the protocol, or those which are a result of an AE that has already been reported.

For purposes of this study, laboratory tests showing a decreased level of FVIII activity should not be reported as adverse events unless there is an impact to clinical outcomes (eg, increased rate of bleeding, worsening of joint disease).

Page 84

10.4.1.5 Pre-existing Conditions

A pre-existing condition is one that is present prior to administration of BMN 270. Such conditions should be recorded as medical history on the appropriate eCRF.

A pre-existing condition should be recorded as an AE or SAE during the study **only** if the frequency, intensity, or character of the condition worsens during the study period. It is important to convey the concept that a pre-existing condition has changed by including applicable language in the verbatim description of the event (eg, *more frequent* headaches).

10.4.1.6 General Physical Examination Findings

At screening, any clinically significant abnormality should be recorded as a pre-existing condition (refer to Section 10.4.1.5). During the study, any new clinically significant findings and/or abnormalities discovered on physical examination that meet the definition of an AE (or an SAE) must be recorded and documented as an AE or SAE on the AE eCRF.

10.4.1.7 Hospitalization, Prolonged Hospitalization, or Surgery

Any AE that results in hospitalization or prolonged hospitalization should be documented and reported as an SAE unless specifically instructed otherwise in this protocol (refer to Section 10.2).

There are some hospitalization scenarios that do not require reporting as an SAE when there is no occurrence of an AE. These scenarios include planned hospitalizations or prolonged hospitalizations to:

- Perform a protocol-mandated efficacy measurement
- Undergo a diagnostic or elective surgical procedure for a pre-existing medical condition that has not worsened
- Insert an in-dwelling IV catheter (such as a Port-a-Cath or other brand, if applicable) for administration of study drug or FVIII replacement therapy
- Receive scheduled therapy (study drug or otherwise) for the study indication

10.4.1.8 **Deaths**

All deaths that occur during the AE reporting period (refer to Section 10.3.1), regardless of attribution, will be recorded on the AE eCRF and expeditiously reported to the Sponsor as an SAE.

When recording a death, the event or condition that caused or contributed to the fatal outcome should be recorded as the single medical concept on the eCRF. If the cause of death

Page 85

is unknown and cannot be ascertained at the time of reporting, record "Unexplained Death" or "Death of Unknown Cause" on the AE eCRF.

10.4.1.9 Pregnancy

Although not an AE per se, pregnancy in the partner of a subject taking trial medication should be reported expeditiously to the Sponsor to facilitate outcome monitoring by the Sponsor. Pregnancy in partner should be reported during the period up to 5 years after viral infusion.

Pregnancy in a partner should be reported within 24 hours of the site becoming aware of the pregnancy by entering the information on the Pregnancy eCRF and submitting to BPV within 24 hours of the site becoming aware of the event. The Investigator must make every effort to follow the subject's partner (with that partner's consent) through resolution of the pregnancy (delivery or termination) and to report the resolution on the Pregnancy Follow-up eCRF. In the event of pregnancy in the partner of a study subject, the Investigator should make every reasonable attempt to obtain the woman's consent for release of protected health information.

Abortion, whether therapeutic or spontaneous, should always be classified as an SAE (as the Sponsor considers these to be medically significant), recorded on the AE eCRF, and expeditiously reported to the Sponsor as an SAE.

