10.1.1 Adverse Events

For this protocol, an adverse event (AE) is any untoward medical occurrence in a subject, temporally associated with the use of study intervention, whether or not considered related to the study intervention.

An AE can therefore be any unfavorable and unintended sign (including an abnormal laboratory finding), symptom, or disease (new or exacerbated) temporally associated with the use of study intervention.

Events meeting the AE definition include:

- Exacerbation of a chronic or intermittent pre-existing condition including either an increase in frequency and/or intensity of the condition.
- New conditions detected or diagnosed after study intervention administration even though it may have been present before the start of the study.
- Signs, symptoms, or the clinical sequelae of a suspected drug-drug interaction.

Events not meeting the AE definition include:

- Any clinically significant abnormal laboratory findings or other abnormal safety assessments which are associated with the underlying disease, unless judged by the investigator to be more severe than expected for the subject's condition.
- The disease/disorder being studied or expected progression, signs, or symptoms of the disease/disorder being studied, unless more severe than expected for the subject's condition.
- Medical or surgical procedure (eg, endoscopy, appendectomy): the condition that leads to the procedure is the AE.
- Situations in which an untoward medical occurrence did not occur (social and/or convenience admission to a hospital).
- Anticipated day-to-day fluctuations of pre-existing disease(s) or condition(s) present or detected at the start of the study that do not worsen.

Page 78

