14.6 Safety Analysis

The Medical Dictionary for Regulatory Activities terminology (MedDRA) will be used by the Sponsor to assign system organ class and preferred term classification to events and diseases, based on the original terms entered on the eCRF.

All AEs will be coded using the current version of MedDRA. The incidence of AEs will be summarized by system organ class, preferred term, relationship to study drug, and severity. A by-subject listing will be provided for those subjects who experience a serious AE (SAE), including death, or experience an AE associated with early withdrawal from the study or study drug.

Clinical laboratory data will be summarized by the type of laboratory test. For each clinical laboratory test, descriptive statistics will be provided on Baseline as well as all subsequent visits. Descriptive statistics for physical examination results and vital signs will also be provided.

Detailed statistical methods will be provided in the SAP.

Page 110

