14.8 Analysis Populations

The intention-to-treat (ITT) population is defined as all subjects who receive BMN 270 infusion, and the modified intention-to-treat (mITT) population is defined as subjects who receive BMN 270 infusion and are HIV-negative. The mITT population will be used for the primary efficacy analysis and ITT will be used for the supportive efficacy analysis. The ITT population will also be used for the safety analysis.

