Regulating Authorities Clinical
Trials (EudraCT) Number:

AAV5-hFVIII-SQ
2017-003215-19
IND #: 017659

Indication: Hemophilia A

Sponsor: BioMarin Pharmaceutical Inc.

PΙ

[name]

Development Phase: Phase 3

Sponsor's Responsible Medical

Monitor:

MD, MSc, MBA

BioMarin Pharmaceutical Inc.

[name]

Duration of Subject

Participation:

Approximately 264 weeks

Dose: 6E13 vg/kg

Study Population: Males aged 18 or older

Date of Original Protocol: 14 August 2017 **Date of Amendment 1 (United** 2 October 2017

States Specific):

Date of Amendment 1 (Global) 25 January 2018

Date of Amendment 2 (Global) 28 June 2018

Date of Amendment 3 (Global) 24 August 2018

Date of Amendment 4 (Global) 9 November 2018

Date of Amendment 5 (Global) 10 May 2019 (unreleased)

Date of Amendment 6 (Global) 3 April 2020

Property of BioMarin CONFIDENTIAL

May not be divulged, published, or otherwise disclosed to others without prior written approval from BioMarin.

This study will be conducted according to the principles of Good Clinical Practice as described in the U.S. Code of Federal Regulations and the International Conference on Harmonisation Guidelines, including the archiving of essential documents

CLINICAL STUDY PROTOCOL AMENDMENT SUMMARY

Amendment 6

Date: 3 April 2020

RATIONALE AND SUMMARY OF CHANGES

Note that global Amendment 5 to the protocol (dated 10 May 2019) was written but never released to health authorities or implemented at any study site. The primary change in global Amendment 5 was a revision of the interim analysis language to allow for the possibility of a second interim analysis. After the first interim analysis was performed in May 2019, it was determined that the second interim analysis would not be needed and, as such, the change contemplated by the protocol amendment would no longer be needed as it would not lead to a change in either the conduct or analysis of the study and its data. The relevant changes from global Amendment 5, including a description of the possible second interim analysis, have been incorporated into Amendment 6.

A summary of major changes covered by Amendment 6 to the 270-301 protocol is provided below. These changes do not affect sample size, endpoint definition, or statistical methods related to the final efficacy analysis of the study:

1. Language concerning the interim analysis has been modified.

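### In a male-only trial, Section 10.4.1.9 sends a partner's abortion to the subject's AE form as an SAE, against the protocol's own AE definition, and nothing shown keeps it out of the subjects' SAE summaries

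*Protocol*

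**What the plan says.** Inclusion criterion 1 (Section 9.3.1) admits men only, and the front matter of Amendment 6 repeats this: "Study Population: Males aged 18 or older".

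Section 10.4.1.9 (Amendment 4) is about partners: "pregnancy in the partner of a subject taking trial medication should be reported expeditiously to the Sponsor". It says that pregnancy is not in itself an AE. It asks for a Pregnancy eCRF within 24 hours, and asks the investigator to follow the partner to delivery or termination and "to report the resolution on the Pregnancy Follow-up eCRF". It then adds: "Abortion, whether therapeutic or spontaneous, should always be classified as an SAE". The reason and the form come next: "as the Sponsor considers these to be medically significant), recorded on the AE eCRF", together with expedited reporting to the sponsor as an SAE.

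Other sections define and analyse these events:

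- Section 10.1.1: "an adverse event (AE) is any untoward medical occurrence in a subject".
- Section 10.2 reaches a subject's child or fetus through one criterion only, congenital anomaly or birth defect.
- Section 14.6 (Amendment 4) codes all AEs from terms entered on the eCRF, summarises their incidence, and adds: "A by-subject listing will be provided for those subjects who experience a serious AE (SAE"), including deaths.
- Section 14.8 (Amendment 4): "The ITT population will also be used for the safety analysis". That population is all infused subjects.

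**The concern.** The rule in Section 10.4.1.9 reads like text written for trials that enrol women, where a subject's own abortion can be her SAE. Here it attaches one person's event to another person's safety record. It also covers elective terminations, which need not reflect harm to anyone.

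SAE incidence is a named safety outcome in the synopsis. If partner events sit among the subjects' SAEs, the listing and possibly the incidence describe something other than what happened to the men who were infused. Investigators would also have to give the event a severity grade and a causality judgement under Section 10.3.3, with no guidance on what these mean when the event is in someone else.

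**Working it through.** The plan states no figure to reproduce. The check is a comparison of sections, followed by one line of arithmetic for scale.

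**Step 1: is the event an AE or SAE under the protocol's definitions?**
- Section 10.1.1 requires an occurrence in a subject. A partner is not a subject, so the condition is not met.
- Section 10.2 extends SAEs to offspring only for a congenital anomaly or birth defect. A partner's abortion as such is not listed.
- Section 10.1.1 also says that a procedure is not itself an AE and that the condition behind it is. For a therapeutic abortion, Section 10.4.1.9 says that the pregnancy is not an AE. An elective termination of an uncomplicated pregnancy would therefore be an SAE with no underlying AE.
- Section 10.4.1.9 classifies the event as an SAE all the same. This is a contradiction in stated text, not a missing detail.

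**Step 2: where does the record go?**
- Section 17 provides eCRFs for each subject. An entry on the AE eCRF therefore carries the male subject's identifier.
- Section 10.4.1.9 already captures the outcome on the Pregnancy Follow-up eCRF, so the event is recorded twice.

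**Step 3: does anything shown take it out again?**
- Section 14.6 works from all AEs on the eCRF and states no exclusion of partner events.
- The protocol writes carve-outs where it wants them: non-serious bleeds (10.1.1.1), some hospitalisations (10.4.1.7) and FVIII declines without clinical impact (10.4.1.4). It writes none for partner events.
- Section 14.6 leaves detailed methods to the SAP, which is not at hand and could exclude them.

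**Step 4: scale.**
- Inputs: N = 130, the approximate number to be dosed (Section 14.7, Amendment 4), and k, the number of affected subjects with no other SAE.
- Formula: increase in SAE incidence = k / N.
- k = 1: 1/130 = 0.77, or about 0.8 percentage points.
- The documents give no rate of partner pregnancy or abortion, so k is unknown. Purely as an assumed range, k from 1 to 4 gives 0.8 to 4/130 = 3.1 points. The upper value needs four different subjects, each with no other SAE, and no exclusion at tabulation.

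**Step 5: does the text still apply?**
- The quoted rule is from Amendment 4. Amendment 6 (3 April 2020) is later, and the text shown stops at the heading of Section 10.3.2, before its pregnancy section.
- Amendment 6's summary of changes names no change to pregnancy reporting, and its AE definition and offspring criterion are the same. It also lists unspecified minor changes, so persistence is likely but not confirmed.

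**The case against.** Section 10.4.1.9 tells sites how to record and expedite an event and does not govern tables. The sections that do govern analysis speak of subjects who experience an SAE and of infused subjects, and a partner is neither. Whether partner records are flagged or dropped at tabulation is ordinary SAP material. The routing also has a stated reason, medical significance, and a practical one: Section 10.5.1 runs 24-hour SAE reporting through the AE eCRF, while Section 10.4.1.9 sets no deadline for the Pregnancy Follow-up eCRF. Moving the event without a replacement would lose the expedited route.

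Much of this stands. Entry into SAE incidence is an inference, the SAP may prevent it, and any fix must keep a 24-hour path. It does not remove the conflict between Sections 10.4.1.9 and 10.1.1, or the assignment to the subject's form. Both are protocol text that a tabulation rule in the SAP would leave in place.

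A reader might go further and infer that pregnancy outcome after paternal exposure will be reported over the wrong denominator, subjects instead of pregnancies. The documents do not support that. No pregnancy-outcome rate over subjects is planned, and the pregnancy forms already collect the reported partner pregnancies that would serve as the denominator.

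**Conclusion.** The point holds as a contradiction in stated text with a likely small effect on safety reporting. Section 10.4.1.9 classifies a partner's abortion as an SAE on the male subject's form, against Section 10.1.1 and beyond the offspring criterion in Section 10.2. Read with Sections 14.6 and 17, this attributes the event to the subject in the SAE listing and, unless the SAP excludes it, in SAE incidence.

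A reader might conclude that the SAE rate is certain to be contaminated. The documents do not establish that, because no section says partner events are counted and the SAP is not shown.

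The size is 0.8 percentage points per affected subject with no other SAE. This assumes about 130 dosed, no exclusion at tabulation, and wording that persists in Amendment 6. No efficacy conclusion is touched, and this is a low-priority correction.

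**What to change.** 1. Check Section 10.4.1.9 of Amendment 6. If the wording persists, reconcile it with Sections 10.1.1 and 10.2.
2. Record partner abortion on the Pregnancy Follow-up eCRF, with an explicit 24-hour submission to the sponsor's pharmacovigilance group, since that form has no deadline now. If the event must stay on the AE eCRF for expediting, add a flag that marks it as a partner event.
3. State in the Safety Analysis section (14.6 in Amendment 4, 14.7 in the Amendment 6 contents) that partner and offspring outcomes are left out of subject AE and SAE incidence and are reported separately. Congenital anomalies remain reportable as SAEs under Section 10.2.

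The cost is a sentence or two in each section, an edit to the eCRF completion guideline, and one small extra table or listing. No safety information is lost, provided the 24-hour route is written in at the same time.

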10.5 Reporting Requirements

10.5.1 Expedited Reporting Requirements

All SAEs and EOSI that occur during the course of the AE Reporting Period (refer to Section 10.3.1), whether or not considered related to study drug, must be reported by entering the information in the AE eCRF and submitting to BPV within 24 hours of the site becoming aware of the event. Investigators should not wait to collect information that fully documents the event before notifying BPV of an SAE. BioMarin may be required to report certain SAEs to regulatory authorities within 7 calendar days of being notified about the event; therefore, it is important that Investigators submit any information requested by BioMarin as soon as it becomes available. IND safety reports will be submitted within 7 calendar days for fatal or life-threatening unexpected suspected adverse reactions (SUSARs) and within 15 calendar days for other non-life-threatening SUSARs

The Sponsor is responsible for identifying, preparing and reporting all SUSARs to the relevant competent authorities, ethics committees and Investigators in accordance with the requirements identified in the Clinical Trials Regulations.

Page 86

If the EDC is unavailable, all SAEs should be reported to BPV by completing the SAE Report Form and faxing or emailing the completed form to BPV within 24 hours of the site becoming aware of the event. Once the EDC is available, the information should be entered in the AE eCRF.

10.5.2 Institutional Review Board or Independent Ethics Committee Reporting Requirements

Reporting of SAEs to the Independent Ethics Committee (IEC) or Institutional Review Board (IRB) will be done in compliance with the standard operating procedures and policies of the IEC/IRB and with applicable regulatory requirements. Adequate documentation must be obtained by BioMarin showing that the IEC/IRB was properly and promptly notified as required.

10.6 Follow-up of Subjects after Adverse Events

After the initial AE/SAE/EOSI report, the Investigator is required to proactively follow each subject at subsequent visits/contacts. All AEs/SAEs/EOSI will be followed until resolution, stabilization, the event is otherwise explained, or the subject is lost to follow-up. Resolution of AEs/SAEs/EOSI (with dates) should be documented on the AE eCRF and submitted to BioMarin Pharmacovigilance and in the subject's medical record to facilitate source data verification.

For some SAEs and EOSI, the Sponsor may follow up by telephone, fax, electronic mail, and/or a monitoring visit to obtain additional case details (eg, hospital discharge summary, consultant report, or autopsy report) deemed necessary to appropriately evaluate the SAE or EOSI report.

10.7 Post-Study Adverse Events

At the last scheduled visit, the Investigator should instruct each subject to report, to the Investigator and/or to BPV directly, any subsequent SAEs that the subject's personal physician(s) believes might be related to prior study drug.

The Investigator should notify the study Sponsor of any death or SAE occurring at any time after a subject has discontinued or terminated study participation, if the Investigator believes that the death or SAE may have been related to prior study drug. The Sponsor should also be notified if the Investigator should become aware of the development of cancer or of a congenital anomaly in a subsequently conceived offspring of a subject that participated in this study.

Page 87

10.8 Urgent Safety Measures

The regulations governing clinical trials state that the Sponsor and Investigator are required to take appropriate urgent safety measures to protect subjects against any immediate hazards that may affect the safety of subjects, and that the appropriate regulatory bodies should be notified according to their respective regulations. According to the European Union (EU) Clinical Trial Directive 2001/20/EC, "...in the light of the circumstances, notably the occurrence of any new event relating to the conduct of the trial or the development of the investigational medicinal product where that new event is likely to affect the safety of the patients, the Sponsor and the Investigator shall take appropriate urgent safety measures to protect the patients against any immediate hazard. The Sponsor shall forthwith inform the competent authorities of those new events and the measures taken and shall ensure that the IRB/IEC/REB is notified at the same time."

The reporting period for these events which may require the implementation of urgent safety measures is the period from the time of signing of the ICF through the completion of the last study visit or at the Early Termination Visit (ETV). Investigators are required to report any events which may require the implementation of urgent safety measures to BioMarin within 24 hours.

Examples of situations that may require urgent safety measures include discovery of the following:

- Lack of study scientific value, or detrimental study conduct or management
- Discovery that the quality or safety of the IP does not meet established safety requirements

Page 88

